2.7.4.2 Vital signs

Analysis of the vital sign measurements using summary statistics for the change from baseline for each post-baseline visit will be performed. These descriptive summaries will be presented by vital sign, treatment group and visit/time. Change from baseline will only be summarized for subjects with both baseline and post-baseline values. Shifts with respect to normal ranges and number and percentage of notable abnormalities will also be summarized.

Clinical notable vital sign values:

- Sitting pulse rate
 - < 50 bpm and 25% decrease from baseline
 - > 100 bpm and 25% increase from baseline
- systolic blood pressure
 - < 90
 - ≥ 140 mmHg
- diastolic blood pressure
 - < 60
 - ≥ 90 mmHg

All vital signs data will be listed by treatment group, subject, and visit/time for patients who ever experience any vital sign abnormalities.

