5.2 Exclusion criteria

Subjects meeting any of the following criteria are not eligible for inclusion in this study:

1. Use of other investigational drugs within 5 half-lives of Screening, or within 30 days (for small molecules) prior to Screening or until the expected pharmacodynamic (PD) effect has returned to baseline (for biologics), whichever is longer; or longer if required by local regulations.
2. History of hypersensitivity to any of the study treatments or its excipients or to drugs of similar chemical classes
3. Subjects having a clearly defined predominant or sole trigger of their chronic urticaria (chronic inducible urticaria) including urticaria factitia (symptomatic dermographism), cold-, heat-, solar-, pressure-, delayed pressure-, aquagenic-, cholinergic-, or contact-urticaria
4. Other diseases with symptoms of urticaria or angioedema, including but not limited to urticaria vasculitis, urticaria pigmentosa, erythema multiforme, mastocytosis, hereditary urticaria, or acquired/drug-induced urticaria
5. Any other skin disease associated with chronic itching that might influence in the investigators opinion the study evaluations and results, eg. atopic dermatitis, bullous pemphigoid, dermatitis herpetiformis, senile pruritus or psoriasis
6. History or current diagnosis of ECG abnormalities indicating significant risk of safety for subjects participating in the study such as:
 - Concomitant clinically significant cardiac arrhythmias, eg sustained ventricular tachycardia, and clinically significant second or third degree AV block without a pacemaker
 - History of familial long QT syndrome or known family history of Torsades de Pointes
 - Resting heart rate (physical exam or 12 lead ECG) < 60 bpm
 - Resting QTcF \geq 450 msec (male) or \geq 460 msec (female) at pretreatment (screening) or inability to determine the QTcF interval
 - Use of agents known to prolong the QT interval unless they can be permanently discontinued for the duration of study
7. Subjects taking medications prohibited by the protocol (see [Section 6.2.2, Table 6-3](#)).
8. History of malignancy of any organ system (other than localized basal cell carcinoma of the skin or in situ cervical cancer), treated or untreated, within the past 5 years, regardless of whether there is evidence of local recurrence or metastases.
9. Pregnant or nursing (lactating) women

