16.1 Appendix 1: Clinically notable laboratory values and vital signs

The following specific criteria have been identified for this study. Should these criteria be met, a re-test must be done within 5 days after the first assessment. Discontinuation of the study treatment should be considered if the abnormal hematology parameter is confirmed:

Hemoglobin: < 10 g/dl

Platelets: < 75 000/mm³

White blood cells: < 3 000/mm³

Neutrophils: < 1 500/mm³

For all other laboratory assessments, the central laboratory will flag laboratory values falling outside of the normal ranges on the central laboratory report (which the investigator should review and sign-off) and the investigator will report any values considered clinically significant in the eCRF.

Notable values for vital signs and change from baseline will be summarized.

Notable values are defined as follows: heart rate of < 60 and > 100 bpm; systolic blood pressure of < 90 and \geq 140 mmHg; diastolic blood pressure of < 60 and \geq 90 mmHg.

For ECGs a notable QTc value is defined as a QTc (Fridericia's) interval of greater than 450 msec for males or greater than 460 msec for females – all such ECGs will be flagged by the central CRO's cardiologist and require assessment for clinical relevance by the investigator.

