2.7.3 Laboratory data

The summary of laboratory evaluations will be presented for two groups of laboratory tests (hematology and serum chemistry).

Descriptive summary statistics for the change from baseline to each study visit will be presented. These descriptive summaries will be presented by test group, laboratory test and treatment group and any LOU064 dose. Change from baseline will only be summarized for subjects with both baseline and post baseline values.

For each parameter, the maximum change from baseline (maximum decrease and maximum increase) will be analyzed analogously.

Laboratory data will be listed and values outside the normal ranges will be flagged by treatment group, subject, and visit/time for patients who have experienced any abnormalities.

In addition, shift tables will be provided for all parameters to compare a subject's baseline laboratory evaluation relative to the most extreme laboratory test value within a treatment period. For the shift tables, the normal laboratory ranges will be used to evaluate whether a particular laboratory test value is normal, low, or high (including category "high and low"). These summaries will be presented by laboratory test and treatment group.

The following laboratory parameters will be analyzed with respect to numerical Common Terminology Criteria for Adverse Event (CTCAE) grades (version 5.0), given in [Table 2-3](#): hemoglobin, platelets, white blood cell count, neutrophils, lymphocytes, creatinine, total bilirubin (TBL), gamma-glutamyl transferase (GGT), alanine aminotransferase (ALT), aspartate aminotransferase (AST), alkaline phosphatase (ALP).

CTCAE grades based on lab results alone will be applied programmatically, Clinical assessments (in *italic* below) will not be considered. In case of missing baseline laboratory assessment, it will be assumed as normal.

The number and percentage of subjects with CTCAE grade newly occurring or worsening after baseline will be presented. Shift tables will be provided on CTCAE grades. These summaries will be split into hematology and chemistry.

Table 2-2 CTCAE grades for laboratory parameters to be analyzed

[figure not shown]
CTCAE term	Laboratory assessment	Grade 1	Grade 2	Grade 3	Grade 4
Anemia	Hemoglobin (Hgb)	<LLN-10.0 g/dL;	<10.0- 8.0 g/dL;	<8.0 g/dL;	Life-threatening consequences;
Platelet count decreased	Platelet	<LLN-75,000/mm ³ ;	<75,000-50,000/mm ³ ;	<50,000-25,000/mm ³ ;	<25,000/mm ³ ;

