2.7.4.3 Liver events

To evaluate potential drug-induced liver injury, newly occurring liver enzyme abnormalities will also be summarized based on the event criteria given below. For potential Hy's Law case, all the elevations must occur at the same post-baseline timepoint. A case will be considered as newly occurring if a criterion is not met or missing at baseline but is met thereafter.

Table 2-3 Liver enzyme abnormalities

Parameter	Criterion
ALT	>3xULN; >5xULN; >8xULN; >10xULN, >20xULN
ALT or AST	>3xULN; >5xULN; >8xULN >10xULN; >20xULN
(ALT or AST) & TBL	>3xULN & (TBL>1.5xULN; >2xULN)
(ALT or AST) & INR	>3xULN & INR>1.5
TBL	>1xULN; >1.5xULN; >2xULN;
ALP	>1.5xULN; >2xULN; >5xULN
ALP & TBL	>3xULN; >5xULN & TBL>2xULN
(ALT or AST) & TBL & ALP	ALT or AST>3xULN & TBL >2xULN & ALP <2xULN (Potential Hy's Law)

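### SAP 2.7.4.2 counts notable blood pressure by absolute limits alone, so subjects already beyond a limit before dosing are counted on treatment with no change; a newly-occurring row is missing.

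*SAP*

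**What the plan says.** SAP 2.7.4.2 plans three summaries for vital signs. One is by visit: "Analysis of the vital sign measurements using summary statistics for the change from baseline for each post-baseline visit will be performed". The other two share a sentence: shifts against normal ranges, and the "number and percentage of notable abnormalities will also be summarized". Subjects with any vital-sign abnormality are also listed by visit.

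The notable limits for blood pressure are absolute: systolic < 90 or >= 140 mmHg, diastolic < 60 or >= 90 mmHg. Protocol Appendix 1 gives the same limits and says "Notable values for vital signs and change from baseline will be summarized". In the same SAP list, pulse must meet a limit and also change, for example "< 50 bpm and 25% decrease from baseline". Blood pressure has no second condition.

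Two other SAP safety tables separate baseline status from what happens afterwards. For liver tests (2.7.4.3): "A case will be considered as newly occurring if a criterion is not met or missing at baseline but is met thereafter". For graded laboratory values (2.7.3): "The number and percentage of subjects with CTCAE grade newly occurring or worsening after baseline will be presented".

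At entry, Protocol 5.2 excludes "Resting heart rate (physical exam or 12 lead ECG) < 60 bpm" and sets QTcF limits. No criterion in 5.1 or 5.2 gives a blood-pressure value. The nearest is exclusion 14, clinically significant disease in the investigator's opinion.

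**The concern.** A subject whose pressure is at or above 140/90 on Day 1 can enrol, stay unchanged for 16 weeks and be counted as a notable abnormality. The by-arm percentage then mixes three things: pressure that was high before the first dose, ordinary visit-to-visit crossing of a fixed limit, and any drug effect. Only the last bears on dose.

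With about 44 subjects per arm and six active arms beside placebo, the first two can blur a real difference or produce an apparent one by chance. The SAP already handles this for liver and laboratory values, so the blood-pressure count is out of line with its neighbours.

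**Working it through.** The plan states no blood-pressure rate or distribution, so there is no figure to reproduce.

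**Inputs from the documents.** The limits are in SAP 2.7.4.2. There are about 44 subjects per arm (Protocol 5). The value at a visit is the mean of three sitting readings (Protocol Table 8-8). The short examination, which includes blood pressure, is done at every visit except screening. That gives Day 1 as baseline and Weeks 2, 4, 8, 12 and 16 as five later looks.

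**Assumed inputs, not from the documents.** Pressures are normal with no drug effect and independent visit noise, and the SD is the total SD at one visit. Only the upper limits are examined.

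| | Low | Middle | High |
|---|---|---|---|
| Systolic mean / SD / within-subject SD | 120 / 12 / 7 | 125 / 14 / 8 | 128 / 15 / 9 |
| Diastolic mean / SD / within-subject SD | 76 / 8 / 5 | 78 / 9 / 6 | 80 / 9 / 6 |

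**Step 1: high at baseline, b.** b = 1 - Phi((limit - mean)/SD).
- Systolic: 1 - Phi(20/12) = 4.8%; 1 - Phi(15/14) = 14.2%; 1 - Phi(12/15) = 21.2%.
- Diastolic: 1 - Phi(14/8) = 4.0%; 1 - Phi(12/9) = 9.1%; 1 - Phi(10/9) = 13.3%.

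With no drug effect, these are also the expected percentages at any single later visit.

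**Step 2: flagged at any of five later visits, a, and share s of those already high at baseline.** By simulation:

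| | Low | Middle | High |
|---|---|---|---|
| Systolic: a | 13.6% | 32.6% | 45.3% |
| Systolic: s | 25% | 37% | 41% |
| Diastolic: a | 12.4% | 25.8% | 34.7% |
| Diastolic: s | 21% | 26% | 30% |

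**Step 3: what a newly-occurring row would show.** Rate among subjects not high at baseline = a(1 - s)/(1 - b).
- Systolic, low scenario: 0.136 x 0.75 / 0.952 = 10.7%. Middle and high: about 24% and 34%.
- Diastolic: about 10%, 21% and 28%.

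So the systolic no-effect rate falls from 14 / 33 / 45% to 11 / 24 / 34%. The remainder is variation around the limit.

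**Step 4: chance imbalance at baseline.** The SD of the difference in b between two arms is sqrt(2b(1 - b)/44). Systolic: 4.6, 7.4 and 8.7 percentage points. Diastolic: 4.2, 6.1 and 7.2 points.

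**Step 5: dilution.** As an illustration only (no test of this table is planned), take 44 against 44, one-sided 5%, and a 15-point excess over placebo. Power = Phi[(0.15 - 1.645 sqrt(2 m(1 - m)/44)) / sqrt((p1(1 - p1) + p2(1 - p2))/44)], where p1 is the background, p2 = p1 + 0.15 and m is their mean. Power is 69% at a background of 5%, 47% at 20% and 41% at 40%.

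**Sensitivity.** If either parameter counts (a composite that the SAP does not define), the three scenarios give 22 / 44 / 57% flagged, of whom 28 / 40 / 46% were already high. A wider grid for the composite used means of 118/74 to 130/82, total SD 14/9, within-subject SD 6/4 to 10/7 and correlation 0.6. It gives 18% to 69% flagged, of whom 20% to 57% were already high. The size is weakly determined.

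**The case against.** The strongest reply is that the table is descriptive and does not stand alone. The same section plans changes from baseline at each visit, shifts, and listings that show each flagged subject's baseline. A pre-existing condition that worsens is captured as a treatment-emergent adverse event (SAP 2.7.1). Averaging three readings removes within-visit noise. Placebo has the same expected background as every active arm. Blood pressure is not among the events of interest named in Protocol 8.4. All of this stands, and it keeps the point minor. It does not make the count itself separate new from old: mean changes do not show how many subjects newly crossed a limit, and the liver and CTCAE tables are descriptive too.

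A reader might infer three stronger things, none of which the documents support.
- **That most of the count is pre-existing hypertension.** In the three scenarios above it is a minority for each parameter, and more subjects cross by variation. Over the wider composite grid the share exceeds half in one of twelve settings. The documents cannot settle it.
- **That the dose comparison is biased.** Randomisation equalises the background on average; what remains is dilution and chance imbalance.
- **That the shift tables cannot help because they use normal ranges.** Neither document gives normal ranges for blood pressure. If the notable limits serve as those ranges, the shift table would already show new occurrence. If not, it would not.

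**Conclusion.** The point holds as a minor one about tabulation. The text alone establishes that notable blood pressure has neither a change condition nor a newly-occurring rule, and that no entry limit keeps out subjects already beyond a limit. Such subjects are counted with no change.

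The size rests entirely on assumed distributions and on counting each parameter at any of five visits; the SAP does not say whether the count is per visit or at any visit. If it is per visit, the expected no-effect percentages are the lower ones in Step 1. The low limits were not sized.

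**What to change.** In SAP 2.7.4.2, add a newly-occurring row for each blood-pressure parameter, worded as in 2.7.4.3: criterion not met or missing at baseline and met at a later visit. The denominator is the subjects not meeting it, or missing, at baseline. Keep the present all-subjects count beside it, so that nothing is lost.

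The cost is one sentence and one filter in the table program. The new row has a smaller denominator. Under the three scenarios it loses about 5% to 21% of subjects for systolic pressure (44 x 0.952 = 41.9 down to 44 x 0.788 = 34.7 per arm) and about 4% to 13% for diastolic (42.2 down to 38.1). On a composite the loss would be about 8% to 29%.

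The row is a partial remedy. Crossing by visit-to-visit variation stays in it and has to be read against placebo. A change condition, as the SAP already uses for pulse, would act on that part; whether to add one, and at what value, is for the sponsor.

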2.7.4.3 Liver events

To evaluate potential drug-induced liver injury, newly occurring liver enzyme abnormalities will also be summarized based on the event criteria given below. For potential Hy's Law case, all the elevations must occur at the same post-baseline timepoint. A case will be considered as newly occurring if a criterion is not met or missing at baseline but is met thereafter.

Table 2-3 Liver enzyme abnormalities

Parameter	Criterion
ALT	>3xULN; >5xULN; >8xULN; >10xULN, >20xULN
ALT or AST	>3xULN; >5xULN; >8xULN >10xULN; >20xULN
(ALT or AST) & TBL	>3xULN & (TBL>1.5xULN; >2xULN)
(ALT or AST) & INR	>3xULN & INR>1.5
TBL	>1xULN; >1.5xULN; >2xULN;
ALP	>1.5xULN; >2xULN; >5xULN
ALP & TBL	>3xULN; >5xULN & TBL>2xULN
(ALT or AST) & TBL & ALP	ALT or AST>3xULN & TBL >2xULN & ALP <2xULN (Potential Hy's Law)

2.8 Pharmacokinetic endpoints

Summary statistics for PK analysis will include mean (arithmetic and geometric), standard deviation (SD), coefficient of variation (CV) (arithmetic and geometric), median, minimum and maximum.

Concentrations below LLOQ will be treated as zero in summary statistics for PK concentration and for PK parameter calculations.

Descriptive summary statistics will be provided for PK concentration by treatment and visit/sampling time point, including the frequency (n, %) of concentrations below the LLOQ.

LOU064 blood concentration data will be listed by treatment, subject, and visit/sampling time point.

Descriptive summary statistics will be provided for PK parameters listed in [Table 2-3](#) by treatment. An exception to this is T_{max} where median, minimum and maximum will be presented.

PK parameters will be listed by treatment and subject.

Table 2-4 pharmacokinetic parameters

AUC_{last}	The AUC from time zero to the last measurable concentration sampling time (t_{last}) (ng x h/mL)
AUC_{tau}	The AUC calculated to the end of a dosing interval (tau) at steady-state (ng x h/mL)
C_{max}	The maximum (peak) observed plasma, blood, serum, or other body fluid drug concentration after single dose administration (ng/mL)
T_{max}	The time to reach maximum (peak) plasma, blood, serum, or other body fluid drug concentration after single dose administration (h)

[figure not shown]
Other PK parameters will be provided if feasible.

2.10 Patient-reported outcomes

Please refer to [section 2.6.1](#) for DLQI analysis.

[figure not shown]

3 Sample size calculation

The sample size calculation is based on the primary endpoint.

The primary objective of this study is to characterize the dose-response relationship among LOU064 q.d. and b.i.d doses (10 mg, 35 mg 100 mg q.d and 10 mg, 25 mg and 100 mg b.i.d) and placebo with respect to change from baseline in UAS7 at Week 4. The sample size was determined with the software R, version 3.0.3.

4 Change to protocol specified analyses

Not applicable.

5 Appendix

5.1 Imputation rules

5.1.1 Study drug

Partial dose date is not allowed in data collection.

5.1.2 AE date imputation

Impute AE end date:

1. If the AE end date 'month' is missing, the imputed end date should be set to the earliest of the (last visit date, 31DECYYYY, date of death).
2. If the AE end date 'day' is missing, the imputed end date should be set to the earliest of the (last visit date, last day of the month, date of death).
3. If AE 'year' is missing or AE is ongoing, the end date will not be imputed.

Impute AE start date:

Before imputing AE start date, find the AE start reference date as below

- If the (imputed) AE end date is complete and the (imputed) AE end date < treatment start date then AE start reference date = min(informed consent date, earliest visit date).

- Else AE start reference date = treatment start date

1. If the AE start date 'year' value is missing, the date uncertainty is too high to impute a rational date. Therefore, if the AE year value is missing, the imputed AE start date is set to NULL.
2. If the AE start date 'year' value is less than the treatment start date year value, the AE started before treatment. Therefore:
 - a. If AE 'month' is missing, the imputed AE start date is set to the mid-year point (01JulYYYY).
 - b. Else if AE 'month' is not missing, the imputed AE start date is set to the mid-month point (15MONYYYY).
3. If the AE start date year value is greater than the treatment start date year value, the AE started after treatment. Therefore:
 - a. If the AE month is missing, the imputed AE start date is set to the year start point (01JanYYYY).
 - b. Else if the AE month is not missing, the imputed AE start date is set to the later of (month start point (01MONYYYY), AE start reference date + 1 day).
4. If the AE start date year value is equal to the treatment start date year value:
 - a. And the AE month is missing the imputed AE start date is set to the AE reference start date + 1 day.
 - b. Else if the AE month is less than the treatment start month, the imputed AE start date is set to the mid-month point (15MONYYYY).
 - c. Else if the AE month is equal to the treatment start date month or greater than the treatment start date month, the imputed AE start date is set to the later of (month start point (01MONYYYY), AE start reference date + 1 day).

If complete (imputed) AE end date is available and the imputed AE start date is greater than the (imputed) AE end date, then imputed AE start date should be set to the (imputed) AE end date.

5.1.3 Concomitant medication date imputation

Impute concomitant medication (CM) end date:

1. If CM end day is missing and CM month/year are non-missing then impute CM day as the minimum of treatment end date and the last day of the month.
2. If CM end day/month are missing and CM year is non-missing then impute CM day as the minimum of treatment end date and the end of the year (31DECYYYY).
3. If imputed CM end date is less than the CM start date, use the CM start date as the imputed CM end date.

Impute CM start date:

1. If the CM start date year value is missing, the imputed CM start date is set to one day prior to treatment start date.
2. If the CM start date year value is less than the treatment start date year value, the CM started before treatment. Therefore:
 - a. If the CM month is missing, the imputed CM start date is set to the mid-year point (01JulYYYY).
 - b. Else if the CM month is not missing, the imputed CM start date is set to the mid-month point (15MONYYYY).
3. If the CM start date year value is greater than the treatment start date year value, the CM started after treatment. Therefore:
 - a. If the CM month is missing, the imputed CM start date is set to the year start point (01JanYYYY).
 - b. Else if the CM month is not missing, the imputed CM start date is set to the month start point (01MONYYYY).
4. If the CM start date year value is equal to the treatment start date year value:
 - a. And the CM month is missing or the CM month is equal to the treatment start date month, then the imputed CM start date is set to one day prior treatment start date.
 - b. Else if the CM month is less than the treatment start date month, the imputed CM start date is set to the mid-month point (15MONYYYY).
 - c. Else if the CM month is greater than the treatment start date month, the imputed CM start date is set to the month start point (01MONYYYY).

If complete (imputed) CM end date is available and the imputed CM start date is greater than the (imputed) CM end date, then imputed CM start date should be set to the (imputed) CM end date.

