6.2 Other treatment(s)

6.2.1 Concomitant therapy

Throughout the study (from Day -14 until Day 113), subjects must take a second generation H1-antihistamine at a locally approved licensed dose and posology (background therapy). Background therapy must not be changed throughout the study. For detailed information on the background medication, refer to the corresponding SmPC.

Prior medication for treatment of CSU will be recorded in the eCRF. In addition, all concomitant medication at screening and prior medication that has been terminated within 4 weeks prior to screening will be recorded. The investigator should instruct the subject to notify the study site about any new medications (including medications that are not related to the treatment of CSU) he/she takes after the subject was enrolled into the study, ideally before initiating a new treatment. All medications, procedures and significant non-drug therapies (including physical therapy and blood transfusions) administered after the subject was enrolled into the study must be recorded on the respective eCRF pages.

Each concomitant drug must be individually assessed against all exclusion criteria/prohibited medication. If in doubt the investigator should contact the Novartis medical advisor before randomizing a subject or allowing a new medication to be started. If the subject is already enrolled, Novartis should be contacted to determine if the subject should continue participation in the study.

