6.2.2 Prohibited medication

Use of the treatments displayed in [Table 6-3](#) are not allowed during the specified time period.

Table 6-3 Prohibited medication

Medication	Prohibition period
Biologics for treatment of CSU (including omalizumab and ligelizumab)	4 months prior to screening until end of study
Routine (daily or every other day during 5 or more consecutive days) doses of systemic corticosteroids	30 days prior to screening until end of study Note: from Day 1 (baseline) until Week 12 (end of treatment period) the use of systemic corticosteroids is not permitted at all.
Leukotriene antagonists (including montelukast and zafirlukast)	From screening until end of study
H2-antihistamines	From screening until end of study
First generation antihistamines	From screening until end of study
Second generation antihistamines other than the defined background medication and rescue medication	From screening until end of study
Other immunosuppressive medication with or without known effect on CSU including but not limited to hydroxychloroquine, methotrexate, cyclosporine A, cyclophosphamide, tacrolimus and mycophenolate mofetil	30 days or 5 half-lives (whichever is longer) prior to screening until end of study

Medication	Prohibition period
Intravenous (i.v.) immunoglobulins or plasmapheresis	30 days prior to screening until end of study
Regular (daily or every other day) doxepin (oral)	14 days prior to screening until end of study
Live attenuated vaccine	6 weeks prior to screening until end of study
Moderate and strong inhibitors of CYP3A4 (see Table 16-5 in Appendix 4), including grapefruit juice	From screening until end of study
Moderate and strong inducers of CYP3A4 (see Table 16-6 in Appendix 4)	From screening until end of study
Any drug known to prolong QTc interval (see https://crediblemeds.org for guidance)	5 half-lives or until pharmacodynamic effect has disappeared prior to baseline (whichever is longer) until end of study
Anti-platelet or anticoagulant medication (for example, warfarin, or clopidogrel or Novel Oral Anti-Coagulant - NOAC) other than acetylsalicylic acid (up to 100 mg/d)	From screening until end of study

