2.4.2 Prior, concomitant and post therapies

Prior urticaria related medication will be summarized by type of therapy and preferred term.

Prior non-urticaria related medication will be summarized by Anatomical Therapeutic Chemical (ATC) code and preferred term for each treatment group.

Background medications will be summarized by Anatomical Therapeutic Chemical (ATC) code, preferred term and dose per administration for each treatment group.

Rescue medications will be summarized by Anatomical Therapeutic Chemical (ATC) code, preferred term and dose per administration for each treatment group.

Concomitant medications other than background or rescue medications will be summarized by Anatomical Therapeutic Chemical (ATC) code and preferred term for each treatment group.

Prior and concomitant significant surgeries and medical procedures will be summarized by primary system organ class and MedDRA preferred term for each treatment group.

Prior medications are defined as treatment taken and stopped prior to first dose of study treatment; Concomitant medications are defined as any medication given at least once between the day of first dose of randomized study treatment and the date of the last study visit.

Medications will be identified using the Novartis Drug and Therapy Dictionary (NovDTD) including the Anatomical Therapeutic Chemical (ATC) code. Medications will be presented in alphabetical order, by ATC code.

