5.1.3.1 Prior therapies date imputation

See [Section 5.1.3](#).

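### A prior therapy whose stop date is known only as the year or month of first dose is always imputed as stopping on or after first dose, so it moves from the prior to the concomitant medication table

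*SAP*

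**What the plan says.** SAP 5.1.3.1, headed "Prior therapies date imputation", contains only a cross-reference to 5.1.3. Three end-date rules there matter:

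- Day missing, month and year known: "impute CM day as the minimum of treatment end date and the last day of the month".
- Day and month missing, year known: "impute CM day as the minimum of treatment end date and the end of the year (31DECYYYY").
- The only floor is the drug's own start date: "If imputed CM end date is less than the CM start date, use the CM start date as the imputed CM end date".

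Nothing in the visible text ties the imputed stop of a prior therapy to the date of first dose.

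SAP 2.4.2 then classifies by date: "Prior medications are defined as treatment taken and stopped prior to first dose of study treatment". Anything given at least once from the day of first dose to the last study visit is concomitant. Prior urticaria medication has its own table, by type of therapy and preferred term. Concomitant medication other than background and rescue has another.

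On collection, Protocol 6.2.1 states: "Prior medication for treatment of CSU will be recorded in the eCRF". Protocol section 3 prohibits all CSU therapies other than the background and rescue antihistamines. Table 6-3 in Protocol 6.2.2 sets pre-screening limits, for example "4 months prior to screening until end of study" for biologics. Exclusion criterion 7 bars subjects who are taking a prohibited medication.

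**The concern.** Choosing the latest plausible stop date is a common convention for a drug that may have continued into the study. For a drug collected as prior therapy in an eligible subject, it overrides something already known, namely that the drug stopped before dosing. The record then does two things it should not. It lowers the prior-therapy count for that arm, which helps the reader judge how treatment-experienced each arm is. It also adds apparent on-study use of a drug that the protocol prohibits, which a reader of the concomitant table would have to explain. Both errors come from a rule as written, so programming it correctly reproduces them.

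**Working it through.** **Inputs.** The end-date rules are from SAP 5.1.3 and the prior and concomitant definitions from SAP 2.4.2. Treatment runs from Day 1 to Day 85 (Protocol section 3). The documents give no first-dose dates, so calendar years 2019 and 2020 are assumed for illustration.

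**Why the result is forced.** Let F be the first-dose date and T the treatment end date, so T ≥ F.

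- Year-only stop in the year of F: imputed stop = min(T, 31 December). Both terms are ≥ F, so the imputed stop is ≥ F.
- Day-missing stop in the month of F: imputed stop = min(T, last day of the month). Again both terms are ≥ F.
- Stop in an earlier year or month: the second term is < F, so the drug stays prior.

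**Check over all dates.** The two years have 365 + 366 = 731 first-dose days. For year-only stops, each day was combined with every treatment length from 1 to 85 days (731 × 85 = 62,135 cases). For month-known stops, treatment was taken as the full 85 days.

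| Stop date known as | Imputed on or after first dose |
|---|---|
| Year of first dose | 62,135 of 62,135 |
| An earlier year (the preceding one was run) | 0 of 62,135 |
| Month of first dose | 731 of 731 |
| An earlier month of the same year | 0 of 4,035 |

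With 85 days of treatment and a year-only stop, the imputed stop is treatment end on 563 of the 731 days and 31 December on 168. The imputed use on or after first dose runs from 1 to 85 days, with a mean of 75.

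**Example.** First dose is 15 Sep 2020, so Day 85 is 15 Sep + 84 days = 8 Dec 2020. With screening 14 days earlier, on 1 Sep, a biologic that respects the 4-month limit stopped by about 1 May. If the stop is recorded only as 2020, the rule gives min(8 Dec 2020, 31 Dec 2020) = 8 Dec 2020. That is 85 days of imputed concomitant use.

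**When the case can arise.** These are shares of the 366 first-dose days of 2020, with screening 14 days before first dose and 4 months taken as 122 days:

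- Biologic, permitted stop in the same year as first dose: (366 − 122 − 14)/366 = 230/366 = 63%.
- Drug with a 30-day limit, permitted stop in the same year: (366 − 30 − 14)/366 = 322/366 = 88%.
- Screening and first dose in the same month, which matters for drugs barred only from screening: (366 − 12 × 14)/366 = 198/366 = 54%.

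The same-month route is closed for permitted stops of biologics and 30-day-limit drugs. Such a stop lies at least 30 + 10 = 40 days before first dose, given the 10-day minimum screening period. For these drugs only the year-only route remains.

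**The case against.** **Sites will usually know the month.** To apply the 4-month and 30-day limits, a site would normally need more than the year of a recent stop, and no stop in an earlier known month moves. This stands as a point about frequency: the problem may affect few records. It does not make the rule right for those it does affect.

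**It may be a deliberate cautious convention.** Counting uncertain exposure as concomitant can be defended, but the SAP does not say that this is intended. Caution about an uncertain stop is also no reason to override one known to precede first dose.

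**A separate form or flag may already split the tables.** That is possible. The visible documents describe none, and the SAP definitions use dates only.

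Some stronger readings are tempting but not supported:

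- A reader might infer that the dose-response result is affected. SAP 2.5.3 uses all available data regardless of rescue or prohibited medication, and no visible text derives protocol deviations from imputed dates.
- A reader might infer that omalizumab history disappears. Previous anti-IgE exposure is a stratification factor and has its own line among the baseline characteristics in SAP 2.3.2. No visible text derives it from imputed dates.
- A reader might take 63%, 88% and 54% as misclassification rates. They are shares of calendar days on which the case is possible.
- A reader might infer that capping at treatment end also misclassifies drugs taken in follow-up. If the start date is complete, the floor at the start date prevents an imputed stop before it. If both dates are partial, the dates may be pulled back to the last dose, but the drug stays concomitant because 2.4.2 counts use up to the last visit.

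**Conclusion.** The point holds, and it is minor. As written, SAP 5.1.3 and 5.1.3.1 misclassify every prior therapy whose stop date is known only as the year, or only as the month, of first dose. The consequence is confined to the descriptive prior and concomitant medication tables: some prior therapies are under-counted and some apparent use of prohibited drugs is created. No estimate, test or analysis set is shown to change. The number of records cannot be stated, because the documents do not say how many stop dates are partial. The conclusion assumes that the date-based definitions in 2.4.2 are applied without an overriding flag.

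**What to change.** Give SAP 5.1.3.1 its own stop-date rule for records collected as prior therapy, or otherwise known to have stopped before first dose:

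- Impute the stop as the earlier of the last day of the known month or year and the day before first dose.
- Do not go before the first day of the known month or year, or before the recorded start date.
- If no date in the known period precedes first dose, query the record.

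In the example this gives min(31 Dec 2020, 14 Sep 2020) = 14 Sep 2020. The date is still only an upper limit, but the drug stays in the prior table. The cap belongs at first dose rather than at informed consent, because 2.4.2 draws the line at first dose and a drug barred only from screening may stop after consent.

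An optional tidy-up is to cap concomitant end dates in 5.1.3 at the last visit or death. This matches the AE rule in 5.1.2 ("the imputed end date should be set to the earliest of the (last visit date, last day of the month, date of death")) and the 2.4.2 window. It does not change the prior or concomitant classification.

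The cost is a few sentences of SAP text and a small programming change. One downside is that an ongoing drug wrongly entered as prior would have to be caught by data query rather than by imputation.
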